Date

Sponsor Summary

Sponsor:	Corindus Vascular Robotics, Inc.
Address:	[name]
Phone Numbers:	[contact]
Primary Contact:	[name], BS
Email:	[contact]
Principal Investigator:	[name], M.D. [name]
Monitoring:	Corindus Vascular Robotics, Inc. [name]
Study Product:	CorPath®GRX + ReMOTE Proof of Principle (POP) System
Protocol Number:	2018-001

GRX with ReMOTE Proof of Principle (POP) Study Summary

Title:	CorPath GRX with ReMOTE Proof of Principle (POP): First in Human
Short Title:	GRX with ReMOTE: First in Human
Device:	
CorPath®GRX + ReMOTE Proof of Principle System (CorPath GRX POP System) consists of:
 
 • CorPath GRX Bedside Unit (Extended Reach Arm, Robotic Drive and single-use Cassette) • Local and Remote Control Station
Regulatory Status:	
The CorPath GRX System (Bedside Unit and Remote Work-space) was granted CM Mark approval on February 29, 2016 and was granted US Food and Drug Administration on October 27, 2016.
 
The Local and Remote Control Station is a validated working prototype.

Indication for Use:	
The CorPath GRX System is intended for use in the remote delivery and manipulation of coronary guidewires, rapid exchange balloon/stent catheters and remote manipulation of guide catheters during percutaneous coronary interventional (PCI) procedures.

Study Objective:	
To evaluate the safety and performance of CorPath GRX POP System, in the ReMOTE (location outside hospital) delivery and manipulation of coronary guidewires and stent/balloon catheters, and manipulation of guide catheters during PCI procedures.

Study Design:	
Prospective, single-arm, single center, non-randomized feasibility study of the CorPath GRX POP System to examine its performance during remote angioplasty (ballooning) and stenting and patient outcomes through 48 hours post-PCI procedure hospital discharge, whichever occurs first.

Principal Investigator:	[name].
Sample Size:	Up to 5 subjects shall be treated in the study.
Investigational Sites:	One (1) international OUS investigative site will participate in this study.
Study Duration/ Follow-up Period:	The anticipated enrollment period is one (1) month. All subjects will be followed post ReMOTE CorPath PCI through 48 hours post-procedure or hospital discharge, whichever occurs first.

Subject Population: Subjects with coronary artery disease and with a clinical indication for PCI.

General Inclusion Criteria: Candidates will be included in the study only if all the following conditions are met:

1. Age \geq 18 years;
2. Patients with coronary artery disease with clinical indication for PCI;
3. Patient deemed appropriate for robotic-assisted PCI; and
4. The subject has been informed of the nature of the study, agrees to its provisions and has provided written informed consent.

Angiographic Inclusion Criteria:

1. Study lesion is a single *de novo* native coronary artery lesion (i.e. a coronary lesion not previously treated).
2. The lesion reference vessel diameter is between 2.50 mm and 4.0 mm by visual estimate.
3. Study lesion length less or equal to 20 mm by visual estimate.
4. The study lesion length can be treated with one stent. The stent should be able to cover the whole length of the lesion with at least 2mm of normal segments on proximal and distal edges of the lesion.
5. Study lesion diameter showing significant stenosis of at least 50% by visual estimate.

NOTE: Patient may have additional lesions requiring treatment using standard PCI (i.e. without utilization of the CorPath device) prior to actual enrollment in the study to perform treatment of study lesion using CorPath device. These non-study lesions must be in different vessel(s) than the study lesion. If non-study lesion(s) are treated on the same day of the index procedure, non-study lesion(s) must be successfully treated prior to the treatment of the study lesion

General Exclusion Criteria: Candidates will be excluded from the study if any of the following conditions are present:

1. Failure/inability/unwillingness to provide informed consent; or
2. The investigator determines that the patient or the coronary anatomy is not suitable for robotic-assisted PCI.

Angiographic Exclusion Criteria:

1. Target lesion that cannot be fully covered by a single stent.
2. Subject requires treatment of multiple lesions
3. Any previous stent placement within 5 mm (proximal or distal) of the target lesion

Procedure Title: CorPath GRX with Remote Study	
Doc Number: 104-07972	
Revision: A	Page: 8 of 39

4. The study lesion requires planned treatment with DCA, laser, rotational atherectomy, or any device except for balloon dilation prior to stent placement

Defined as the time measured from the insertion of the hemostasis sheath until procedure complete (guide catheter removed).

PCI Procedure Time:

Defined as the time measured from the insertion of the guide catheter until the removal of the guide catheter.

CorPath GRX Procedure Time:

Defined as the time measured from the exit of the guide wire from the guide catheter until the guidewire is retrieved into the guide catheter.

Procedure Title: CorPath GRX with Remote Study	
Doc Number: 104-07972	
Revision: A	Page: 10 of 39

Revision History

Version	Version Date	Summary of Changes
A	TBD	
Initial release

1.0 Introduction

1.1 Device Name

CorPath®GRX + ReMOTE Proof of Principle System (CorPath GRX POP System)

1.2 Background

The use of surgical robotics is growing immensely. Part of the reason for this growth is the amount of benefits afforded by robotics that are absent in traditional operative methods. For example, robots offer stability, accuracy, integration with modern imaging technology, greater range of motion, telesurgery, in addition to multiple other benefits inherent to individual surgical specialties [1]. Since the introduction of robotic surgery, many advances have been made in the field. One such advancement is using robots to perform operations remotely over long distances. In 2001, surgeons working in New York successfully used remotely controlled robots to laparoscopically remove a gall bladder from a 68-year-old woman in Strasbourg, France. The doctor moved a (remote) control in his hand in New York that sent a signal to (France) to move the robotic arm. So, when the doctor moved the robotic hand (using the remote control) in New York, the hand moved in the patient in France [2].

The CorPath GRX System is the second generation of the CorPath platform. With CorPath GRX, workflow is streamlined by the addition of an easily positioned extended reach arm. The new arm incorporates a "touchscreen". The benefits of the touchscreen allow the tableside user to visualize the instructions. Workflow enhancements also include a redesigned cassette to allow for active guide management. The clinical improvements consist of the addition of Active Guide Management, faster guidewire rotation and improved measurement accuracy. These improvements have the potential to allow for greater robotic procedural control for the primary operator and, perhaps a reduction in not only operator but also patient and Cath Lab team radiation exposure.

Currently the CorPath GRX consists of a bedside unit cabled to the robotic arm in the room of a procedure suite. The cabling is short enough to allow the physician operator to transmit intricate movements of the guidewire, balloon or stent with minimal latency. The Strasburg, France case above has set the stage for remote robotic-PCI. Today's LAN/MAN/WAN communication infrastructure is robust enough to allow remote medical procedures to become commonplace. Although robotic PCI has not yet been performed with an operator located off-site, the recently published REMOTE-PCI study demonstrated the feasibility of such an approach [3].

This study will evaluate the CorPath GRX POP System which will be modified to work remotely over larger distances utilizing LAN/MAN/WAN connectivity. Currently the CorPath GRX has two major components: a cockpit and a robotic arm (which are connected via several cables). This system allows an interventional cardiologist to advance and deploy coronary balloons and stents while sitting at the cockpit instead of standing at the side of the procedure table. After modifying the system to work remotely, the interventional cardiologist will be advancing and deploying balloons and stents remotely while the patient is in another room or tertiary care center (kilometers away).

The CorPath GRX POP System contains two identical workspaces, a local (Cath Lab) workspace designed for bedside use, and a remote workspace, designed for use by an off-site interventionalist. In this study, the primary Cath Lab will have a workspace, and this is the location of the secondary physician operator, scrub technologist and patient. The primary physician operator will be offsite at another location with access and control of the second workspace. The two workspaces equipment will communicate through LAN/MAN/WAN connectivity. The two workspaces will be outfitted with a telepresence system that will allow for real time audio and video between the primary Cath Lab and off-site primary operator during the remote PCI procedure.

This study will examine the feasibility of the CorPath GRX POP System during remote robotic-assisted PCI.

2.0 Intended Use & Device Description

2.1 Intended Use

The CorPath GRX System is intended for use in the remote delivery and manipulation of coronary guidewires, rapid exchange balloon/stent catheters and remote manipulation of guide catheters during percutaneous coronary interventional (PCI) procedures. The Local and Remote Control Station is a validated working prototype.

2.2 Device Description

The CorPath Bedside Unit consists of three components: (1) Extended Reach Arm, (2) Robotic Drive and (3) single-use Cassette ("Cassette"). The Extended Reach Arm supports the Robotic Drive, which houses the Cassette. The joysticks on the Control Console remotely deliver signals through a communication cable to the Robotic Drive that operates the Cassette. After the

selected guidewire and catheter are loaded into the Cassette, the Cassette translates the signals from the joystick manipulations into the linear and rotational movements of the guidewire and guide catheter and the linear movements of the balloon/stent. The Cassette has a Y-connector holder which holds the guide catheter hub and is attached to the drive gear and CoPilot. The drive gear enables guide catheter rotation.

The CorPath GRX POP System is comprised of the CorPath GRX Bedside Unit and the addition of two workspaces. One workspace is a local (Cath Lab) workspace designed for bedside use, and the second is a remote workspace, designed for use by an off-site interventionalist. Each workspace is comprised of two major subsystems: a robot control subsystem, and a telepresence subsystem.

The robot control subsystem contains a control console, housing a touch-screen and three joysticks (one joystick for balloon/stent manipulation, one joystick for guidewire manipulation and one joystick for guide catheter manipulation). The balloon/stent joystick allows for precise control of linear motion (advancement and retrieval) of its respective devices. The guidewire joystick allows for both linear and rotational movement (clockwise and counterclockwise) of the guidewire. The guide catheter joystick allows for precise control of linear motion (advancement and retrieval) and for rotational movement (clockwise and counterclockwise) of the guide catheter. The devices are controlled independently, which allows operations to be performed individually (by using one joystick at a time) or simultaneously (by activating multiple joysticks at once). For precise, discrete manipulation, the balloon/stent, guidewire and guide catheter can also be manipulated in discreet 1-mm increments via the touch-screen buttons on the Control Console.

The robot control subsystem also includes monitors for hemodynamic data and fluoroscopic video, providing the operator enhanced visualization of the PCI procedure.

The telepresence system contains local and remote cameras, monitors, and conferencing hubs, which are independent from the robot control subsystem, and provide human-to-human communication. The telepresence subsystem enables full bi-directional audio and video communications between the remote interventional cardiologist, and the Cath lab team. A real-time data stream allows seamless and instantaneous collaboration between the local and remote teams.

CorPath Use Technique

The operator should refer to the CorPath GRX System Operator's Manual for a detailed description of the system and relevant techniques.

To obtain proper data for analysis, the following procedure, with associated data collection milestones, is recommended, but in no case, dictates use of the CorPath GRX POP System in a manner different from that presented in the Operator's Manual.

Note that control of the system is identical whether operated from the local or remote workspace. Only one workspace can be active at a time.

3.0 Objectives, Feasibility and Safety Endpoints

3.1 Primary Objective

The primary objective of the GRX with ReMOTE Study is to evaluate the safety and performance of the CorPath GRX POP System, in the ReMOTE delivery and manipulation of coronary guidewires and balloon/stent catheters, and manipulation of guide catheters during PCI procedures.

3.2 Feasibility and Safety Endpoints

The following primary and secondary endpoints will be evaluated in patients enrolled in the CorPath GRW POP Study. Parameters are subject-based or lesion-based.

3.2.1 Primary Feasibility Endpoint – Device Technical Success

Defined as *successful* completion of the ReMOTE robotic-assisted PCI absent **unplanned** conversion to manual for guidewire or balloon/stent catheter inability to navigate vessel anatomy or poor guide catheter support.

3.2.2 Primary Safety Endpoint – In hospital MACE

MACE is defined as cardiac death, clinically relevant MI after coronary revascularization (Q-wave or non-Q-wave myocardial infarction), or clinically driven target vessel revascularization (TVR) by PCI or CABG. Clinically relevant MI after coronary revascularization is defined as:

- Patients with normal baseline cardiac biomarkers
 - CK-MB ≥ 10 x ULN or cTn (I or T) ≥ 70 x ULN, or
 - CK-MB ≥ 5 x ULN or cTn ≥ 35 x ULN plus new Q-waves in ≥ 2 contiguous leads or LBBB
- Patients with elevated baseline cardiac biomarkers
 - Baseline biomarkers are stable or falling:
 - CK-MB ≥ 10 x ULN or cTn (I or T) ≥ 70 x ULN of **most recent pre-procedure level**, or
 - CK-MB ≥ 5 x ULN or cTn ≥ 35 x ULN of **most recent pre-procedure level** plus new Q-waves in ≥ 2 contiguous leads or LBBB
 - Baseline biomarkers have not been shown to be stable or falling: CK-MB (or cTn) rises by an absolute increment equal to those recommended above plus new ST-

segment elevation or depression plus signs consistent with a clinically relevant MI, such as new onset or worsening heart failure or sustained hypotension.

Note: Post PCI collection of biomarkers is left to the discretion of the investigator based on local practice patterns and clinical indication and is not mandatory by protocol.

3.2.3 Secondary Feasibility Endpoint – Clinical Success

Defined as less than 30% residual stenosis (visual estimate) post PCI in the lesion(s) treated with the CorPath GRX POP System (without an unplanned switch to the manual procedure) in the absence of device-related SAE, either within forty-eight (48) hours of the procedure or prior to hospital discharge, whichever occurs first.

3.3 Safety Measure

A safety-based measure will also be utilized to confirm the overall safety of the procedures involving the CorPath GRX POP System. This measure will include:

3.3.1 Serious Adverse Events

All Serious Adverse Events (SAEs) from the start of the ReMOTE robotic-assisted PCI procedure until the end of the study will be summarized.

3.4 Procedural Characteristics

The objective of this study is to demonstrate remote angioplasty (ballooning) and remote stenting with the use of the CorPath GRX POP System.

3.4.1 Overall Procedure Time Measure

Defined as the time measured from the insertion of the hemostasis sheath until the removal of the guide catheter

3.4.2 PCI Procedure Time

Defined as the time measured from the insertion of the guide catheter until removal of the guide catheter.

3.4.3 Fluoroscopy Time

Total fluoroscopy utilized during the PCI procedure, as recorded by an imaging system.

3.4.4 Patient Radiation Exposure

DAP (dose-area-product) and cumulative dose/air kerma, as recorded during the PCI procedure.

3.4.5 Contrast Fluid Volume

Total volume used during the PCI procedure.

4.0 Investigational Plan

4.1 Overview

This is a prospective, single-arm, single center, non-randomized feasibility study of the CorPath GRX POP System to examine its performance during remote angioplasty (ballooning) and stenting and patient outcomes through 48 hours post-PCI procedure.

The study population will consist of up to five (5) staged subjects undergoing a PCI procedure with the CorPath GRX POP System who provide informed consent.

The study will be conducted at one (1) international (OUS) site with an enrollment of up to 5 subjects. This study protocol does not dictate the therapeutic decisions of the operator.

All enrolled patients will be followed post- ReMOTE robotic-assisted PCI procedure through hospital discharge or 48 hours, whichever occurs first.

4.2 Enrollment Plans

Each staged patient undergoing a ReMOTE robotic-assisted PCI procedure will be enrolled in the study after providing written informed consent for the provision of data.

4.3 Informed Consent Procedures

When a suitable candidate presenting for a percutaneous coronary intervention meets the eligibility criteria for enrollment in this study, the Investigator (or designee) will explain the risks and benefits of data provision to the subject. If the subject agrees to participate in the study, an approved study-specific informed consent form must be signed.

During the informed consent discussion, the background of the proposed study and the benefits and risks of the study should be explained to the subject, per the site's Informed Consent Process. This discussion should highlight the fact that the patient is being asked solely to share the data collected from their procedure and any related events through 48 hours post-procedure or discharge, whichever occurs first.

Once the subject signs the EC-approved consent form, they are considered enrolled in the study. Failure to obtain signed informed consent renders the subject ineligible. Copies of the signed informed consent shall be kept in the subject's medical records and study files. A copy of the fully executed informed consent form must be given to each subject enrolled in the study.

Modifications to the GRX with ReMOTE Study Informed Consent must have written approval by Corindus and the EC prior to use, as required.

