4.5 Patient Selection

Subjects with coronary artery disease with a clinical indication for PCI and deemed appropriate for PCI with the CorPath GRX POP System, and who have signed the ICF for data collection will be enrolled into the GRX with ReMOTE study.

General Inclusion Criteria:

1. Age \geq 18 years;
2. Patients with coronary artery disease with clinical indication for PCI;
3. Patient deemed appropriate for the CorPath GRX POP System; and
4. The subject has been informed of the nature of the study, agrees to its provisions and has provided written informed consent.

Angiographic Inclusion Criteria:

1. Study lesion is a single *de novo* native coronary artery lesion (i.e. a coronary lesion not previously treated).
2. The lesion reference vessel diameter is between 2.50 mm and 4.0 mm by visual estimate.
3. Study lesion length less or equal to 20 mm by visual estimate.
4. The study lesion length can be treated with one stent. The stent should be able to cover the whole length of the lesion with at least 2mm of normal segments on proximal and distal edges of the lesion.
5. Study lesion diameter showing significant stenosis of at least 50% by visual estimate.

NOTE: Patient may have additional lesions requiring treatment using standard PCI (i.e. without utilization of the CorPath device) prior to actual enrollment in the study to perform treatment of study lesion using CorPath device. These non-study lesions must be in different vessel(s) than the study lesion. If non-study lesion(s) are treated on the same day of the index procedure, non-study lesion(s) must be successfully treated prior to the treatment of the study lesion.

General Exclusion Criteria:

1. Failure/inability/unwillingness to provide informed consent; or
2. The investigator determines that the patient or the coronary anatomy is not suitable for robotic-assisted PCI.

Angiographic Exclusion Criteria:

1. Target lesion that cannot be fully covered by a single stent.
2. Subject requires treatment of multiple lesions
3. Any previous stent placement within 5 mm (proximal or distal) of the target lesion.
4. The study lesion requires planned treatment with DCA, laser, rotational atherectomy, or any device except for balloon dilatation prior to stent placement.
5. The study vessel has evidence of intraluminal thrombus or moderate to severe tortuosity (> 90°) proximal to the target lesion.
6. The study lesion has any of the following characteristics:
 - a. Total occlusion

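### Section 4.3 tells the investigator to present participation as data sharing only, although the study itself delivers first-in-human remote PCI with an investigational control system

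*Combined protocol and SAP*

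**What the plan says.** Section 4.3 has two relevant paragraphs. In the first, the investigator or designee "will explain the risks and benefits of data provision to the subject", and then: "If the subject agrees to participate in the study, an approved study-specific informed consent form must be signed". In the second, "the background of the proposed study and the benefits and risks of the study should be explained to the subject", following the site's own consent process. The next sentence says the discussion should highlight that "the patient is being asked solely to share the data collected from their procedure and any related events", up to 48 hours after the procedure or discharge, whichever is earlier.

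Neighbouring sections describe consent in similar terms but without the exclusive word. Section 4.2 refers to "written informed consent for the provision of data", and 4.5 to subjects "who have signed the ICF for data collection will be enrolled into the GRX with ReMOTE study". Section 7.1 describes the subjects as receiving standard treatments and procedures.

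Other text is broader. General inclusion criterion 4 in 4.5 reads "The subject has been informed of the nature of the study, agrees to its provisions and has provided written informed consent". Section 4.1 describes the population as "staged subjects undergoing a PCI procedure with the CorPath GRX POP System who provide informed consent".

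**The concern.** An instruction to highlight that the patient is asked only for data suits a registry, where the procedure would take place anyway and the study merely records it. If the study is the reason the procedure takes place, the instruction leaves out the main thing being asked. An investigator who followed 4.3 to the letter would give that incomplete account as the prominent message of the discussion, to every subject. What is at stake is the patient's understanding of participation. The trial's results are not at stake.

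**Working it through.** No arithmetic applies and the plan gives no figure to reproduce. The test is whether the remote procedure is routine care that the study observes, or something the study delivers. Only in the first case is *solely* accurate.

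**Text that makes the procedure part of the study**

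- Study Summary: the title calls the trial first in human, and the sample size entry speaks of up to 5 subjects being treated in the study.
- Section 1.2: the current system is cabled within the procedure suite. It is to be modified to work over larger distances, with the primary operator off-site. Robotic PCI with an off-site operator is said not to have been done yet.
- Section 3.4: the stated objective is to demonstrate remote ballooning and remote stenting with this system.
- Note to the angiographic inclusion criteria in 4.5: enrollment is for the purpose of treating the study lesion with the device.
- Section 4.4: someone who signs the consent form and then has no remote procedure is a screen failure. Consent therefore comes before the procedure and is not a later release of routine records.
- Sections 2.1, 10.1 and 10.2: the Local and Remote Control Station is a validated working prototype. The control system is shipped as an investigational device, only to the participating site and only after regulatory and EC approval to begin. At the site, investigational devices are available only to authorised staff and to subjects under the investigator's supervision.

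**Text that points to data collection on routine care**

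- Section 4.3, first paragraph and the *solely* sentence.
- Sections 4.2 and 4.5: consent for data, but not worded as exclusive.
- Section 7.1: standard treatments and procedures.
- Section 4.1: the protocol does not dictate the operator's therapeutic decisions. Its description of the population could, taken alone, fit either reading.

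**Weighing the two.** The first list decides the question. A procedure not previously done by an off-site operator, on equipment supplied only for this study, is not care the patient would receive regardless. The documents describe no route to it outside the study. So *solely* does not match what enrollment involves.

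**Within 4.3.** The first paragraph names the risks and benefits of providing data; the second names those of the study. These differ in scope. The second-paragraph sentences do different jobs, however: one says what must be explained, the other what the patient is asked for. Both can be carried out in one discussion. The internal defect is a mismatch of scope, weaker than the conflict with the design.

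**The case against.** The best defence reads the disputed sentence narrowly. With its 48-hour limit, it may mean only that nothing is asked of the patient beyond peri-procedural data. Section 4.7 supports this, since no further patient contact is required, and 4.6.1 and 4.8 describe much of the data as routine. The base CorPath GRX System is described as approved, the control station as validated, and 1.2 goes on to cite a published study as having shown the feasibility of the approach. Several safeguards also apply: the site's consent process (4.3), inclusion criterion 4, Good Clinical Practice and all applicable regulations (9.0), EC approval of the consent form (9.1), and regulatory and EC approval before devices are shipped (10.1).

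Much of this stands as a limit on the consequence. It does not rescue the sentence. The narrow reading explains why follow-up is light, but the patient is still asked to undergo the procedure. Approval of the base system does not extend to the control system that 10.1 calls investigational. The safeguards leave the instruction in place: 9.0 lists the protocol alongside the regulations as part of conduct under Good Clinical Practice and does not say which prevails.

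A reader might infer that 4.3 flatly contradicts itself, or that it leaves out risk disclosure. The documents do not support either reading: the benefits and risks of the study must be explained, and the sentence requiring this stands directly before the disputed one.

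**Conclusion.** The point holds as a conflict between the instruction in 4.3 and the interventional design, with a lesser inconsistency of scope inside 4.3. Confidence in that wording conflict is high. It reaches the consent discussion of every subject, up to 5 at one site. The exclusive wording occurs only in 4.3. No endpoint, estimate or analysis changes.

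A reader might go further and infer that subjects' consent was defective. That is not shown. The consent form was not available to this review, the content of the site's consent process is not in the documents, and the approvals required by 9.1 and 10.1 may well have secured a full description. The finding concerns only what the protocol tells the investigator to say. It rests on taking the protocol's own account of the device's status and the procedure's novelty at face value. The change should be made because a written rule, followed exactly, would misdescribe participation, and correcting it is easy.

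**What to change.** In 4.3, delete *solely*, state that participation covers both undergoing the investigational remote procedure and sharing the resulting data, and make the first paragraph refer to the risks and benefits of the study instead of those of data provision. Bring the consent phrases in 4.2 and 4.5, and the reference to standard treatments in 7.1, into line with the interventional design. Leave the detailed disclosure content to the EC-approved consent form, and check that form once for consistency with the revised text.

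The cost is wording changes in four sections, one document check, and the sponsor and EC approval that 9.1 already requires for any protocol change. No patients, procedures or data items are added.
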